8.9. Contraception

Andexanet is not expected to have reproductive or developmental toxicity based on the following: 1) andexanet is intended for single-dose administration and, therefore, has limited potential for reproductive or developmental toxicity; 2) andexanet is a biotechnology-derived protein that is a modification of an endogenous protein in the coagulation cascade (FXa); 3) andexanet has a very short half-life (1- to 2-hour effective half-life); and 4) andexanet was designed as a universal antidote for FXa inhibitors, which are prescribed primarily in elderly patient populations that are not of reproductive capacity. Andexanet is not expected to interact with hormone contraception.

Nevertheless, one of the following highly effective birth control methods is recommended for female patients of childbearing potential for the entire duration of the trial and for at least 1 month after study drug administration:

- Combined (estrogen- and progestogen-containing) hormonal contraception associated with inhibition of ovulation:
 - Oral
 - Intravaginal
 - Transdermal
- Progestogen-only hormonal contraception associated with inhibition of ovulation:
 - Oral
 - Injectable
 - Implantable
- Intrauterine device
- Intrauterine hormone-releasing system
- Bilateral tubal occlusion
- Successfully vasectomized partner
- Sexual abstinence

Male patients with female sexual partners who are pregnant or of childbearing potential must use one acceptable method of contraception, including a barrier method (e.g., condom), for the entire duration of the study and for at least 1 month following study drug administration. Also, male patients must refrain from attempting to father a child or donating sperm for 1 month following study drug administration. Periodic abstinence (e.g., calendar, ovulation, symptothermal, post-ovulation methods) and withdrawal are not acceptable methods of contraception.

Acceptable birth control methods are those that result in a failure rate of more than 1% per year. These methods include progestogen-only oral hormonal contraception, where inhibition of ovulation is not the primary mode of action; male or female condom with or without spermicide cap; and diaphragm or sponge with spermicide. A combination of male condom with either cap, diaphragm, or sponge with spermicide (double barrier methods) are also considered acceptable but are not highly effective birth control methods.

8.9.1. Pregnancy Reporting

If a woman who is a study patient becomes pregnant or a woman suspects she is pregnant from a male study patient, the Investigator should be informed immediately. The Sponsor must, in turn, also be notified by the Investigator immediately (no more than 24 hours after learning of the pregnancy) by completing a Pregnancy CRF and a Pregnancy/Breastfeeding Reporting and Outcome form. In the event a female patient of a male patient is pregnant or suspects she is pregnant by the male patient, the male patient will be advised by the study Investigator to have his pregnant partner inform her treating physician immediately. The pregnancy Follow-up form. For any abnormal fetal outcome, including congenital anomaly or birth defect, spontaneous or therapeutic abortion, stillbirth, pre-mature birth, or other outcome other than live normal birth, the Investigator should immediately report to the Sponsor the abnormal fetal outcome on an SAE form.

9.0 STUDY ASSESSMENTS

Details on the collection, processing, storage, and shipment of samples are contained in the Laboratory Manual.

9.1. Efficacy Assessments

9.1.1. Effective Hemostasis

Effective hemostasis is a composite endpoint based on image evaluation (CT or MRI), NIHSS score, and use of rescue therapy. Imaging is to be performed at baseline and approximately 12 hours post-randomization, and should utilize a consistent imaging modality for both time-points to minimize technical discrepancy (i.e., CT or MRI scan). However, additional imaging may be performed at any time during the study per Investigator discretion and should be considered in the case of clinical deterioration. NIHSS evaluation (blinded or unblinded) to inform hemostatic efficacy will be performed at baseline (prior to randomization) and at 2 hours, 3 hours, 6 hours, and 72 hours post-randomization. Blinded NIHSS evaluation will occur at 12 hours and 24 hours post-randomization to minimize bias. As with brain imaging, additional assessments may be performed at any time. Use of rescue therapy (including procedures intended to treat the hematoma), as defined in Section 7.2, Section 7.3, and Section 7.4, between 3 hours and 12 hours following randomization will be considered a treatment failure (i.e., poor/none hemostatic efficacy).

9.1.2. Anti-fXa Activity

Anti-fXa activity will be measured from plasma samples to assess the anticoagulant status of FXa inhibitors using a modified chromogenic assay performed at a Central Laboratory. Anti-fXa activity will be evaluated at baseline, and at 1- and 2-hours post-randomization.

9.1.3. Thrombin Generation

Thrombin generation will be measured from plasma samples to assess the anticoagulant effect of FXa inhibitors. Tissue factor-dependent thrombin generation will be performed at a Central Laboratory. Five parameters related to thrombin generation are measured: Endogenous Thrombin Potential (ETP), peak height, time to peak height, lag time, and velocity index. ETP is prospectively identified as the primary measure for thrombin generation. Thrombin generation will be assessed at baseline, and at 1- and 12-hours post-randomization.

9.1.4. Glasgow Coma Scale (GCS) Score

GCS evaluation (blinded or unblinded) will be performed at baseline (prior to randomization) and at 2 hours, 3 hours, 6 hours and 72 hours post-randomization. Blinded GCS evaluation will occur at 12 hours and 24 hours post-randomization.

9.1.5. Modified Rankin Scale

An mRS score will be obtained at baseline (pre-morbid), at 30 days post-randomization or at the Early Termination visit. If the baseline mRS is unavailable during screening, the mRS can be collected from either the patient, relative, care giver, or LAR at a post-randomization timepoint as long as the mRS reflects the patient's pre-morbid (i.e., pre- ICrH) neurological status. The pre-morbid mRS score should reflect the patient's neurological status prior to acute illness. The utility-weighted mRS (uw-mRS) is a quality-of-life measure ensuring that the mRS score reflects both treatment effect and patient perception. In the uw-mRS, utilities based on the EuroQol Group 5-Dimension (EQ-5D) questionnaire values are assigned to the mRS health states.

9.1.6. EQ-5D (EuroQol-5 Dimension)

A five-dimension health-related quality of life measure for clinical and economic appraisal will be obtained at 30 days post-randomization or at the Early Termination visit.

9.2. Safety Assessments (other than Adverse Events)

9.2.1. Vital Signs, Height, and Weight

Vital signs include temperature, SBP, Diastolic Blood Pressure (DBP), Heart Rate, and Respiratory Rate.

Height and weight will be recorded at screening and baseline. If it is not possible to measure height or weight, a reported height or weight, or a recent height or weight from the medical record is acceptable.

9.2.2. Clinical Laboratory Testing

Blood specimens for routine chemistry and hematology will be obtained at selected time-points (see Appendix A).

The following assays will be performed at the Local Laboratory (as available):

- Hematology: hemoglobin, hematocrit, White Blood Cell (WBC) count, platelet count, WBC differential
- Coagulation: International Normalized Ratio (INR)
- Serum Chemistry: sodium, potassium, chloride, carbon dioxide (bicarbonate), glucose, blood urea nitrogen, creatinine, aspartate aminotransferase, alanine aminotransferase, albumin, alkaline phosphatase, calcium, phosphorus, and total, direct, and indirect bilirubin
- Serum or urine pregnancy test (in females of childbearing potential; see Appendix J)
- Anti-fXa activity (for patients treated with an oral FXa inhibitor > 15 hours prior to randomization or unknown time of last dose). Note: Measurements of anti-fXa

activity after initiation of andexanet are discouraged because of assay interference with andexanet. Please consult the Laboratory Manual for further details.

Local Laboratory assays of hematology, coagulation, and serum chemistry are not required for the purpose of eligibility. However, complete panels should not be missed at screening/baseline because these assays inform the investigator of suitability of the patient for the study (e.g., multiorgan failure, metabolic or hematological abnormalities).

The following assays will be performed at a Central Laboratory:

- Anti-fXa activity (Note: evaluation of the secondary efficacy endpoint will use only central, and not local, anti-fXa activity)
- Antibodies to FX, FXa, and and exanet
- Neutralizing antibodies to FX, FXa, and and exanet
- Thrombin generation

The multiple samples collected within a narrow window of time $(\pm 15 \text{ min})$ from baseline through to the first 2 to 3 hours are critical for the Central Lab's assessment of and examet activity.

9.2.2.1. Exploratory Biomarker Assessments

Samples for tissue factor pathway inhibitor (TFPI) activity or other future exploratory biomarker research will also be obtained at selected time-points (see Appendix A).

TFPI, an endogenous inhibitor of fXa and known to interact with andexanet, will be measured using Antichrome[®]-TFPI Chromogenic assay at a Central Laboratory. TFPI will be evaluated at baseline, 1-, 2-, and 12-hours post-randomization and at the 30 day follow-up visit.

10.0 STATISTICAL CONSIDERATIONS AND DATA ANALYSIS

The Study Objectives and Study Design are described in Section 2.0 and Section 3.1, respectively. The information in this section is a summary of the planned statistical analyses.

10.1. General Considerations

During the conduct of the study, the Sponsor and Investigators will be blinded to the aggregated efficacy and safety summaries. Also, all unblinded analyses that are required to support the DSMB will be performed by an independent unblinded statistician. These analyses will be performed under the direction of the DSMB according to the Statistical Analysis Plan (SAP) and the DSMB Charter. The results of these unblinded analyses will not be available to the Sponsor or Investigators until after database lock, unless the DSMB recommends early termination of the trial.

The safety interim analyses will follow the same procedures as the efficacy interim analysis (see Section 10.7), with the Sponsor remaining blinded to the results of these analyses unless the DSMB recommends stopping the trial early.

Once the study is complete and the final database lock is performed, the study will be fully unblinded and final analyses will be performed.

All efficacy hypothesis tests will be 2-sided and performed at the 0.05 significance level. Adjustments for the overall type I error for the planned interim efficacy analysis are described in Section 10.7.

It is anticipated that statistical summaries will be performed using SAS Version 9.2 (SAS Institute, Inc., Cary, NC, USA) or higher. Additional software may be used for the production of graphics and for statistical methodology not available in SAS.

All efficacy and safety endpoint parameters will be summarized descriptively.

10.2. Randomization

This is a prospective, randomized, open-label study, with blinded assessment of efficacy and safety (TEs and deaths) outcomes by the independent EAC. Patients will be randomized 1:1 to and exanet or usual care, stratified by the Investigator's intended-usual-care-agent, determined on a patient-by-patient basis, as well as time from symptom onset to baseline imaging scan.

10.3. Determination of Sample Size

Hemostatic efficacy was reported by Sarode et al [7] as 58.3% (95% CI 27.7, 84.8) and 41.7% (95% CI 15.2, 72.3) for a small sample of ICrH patients receiving FFP and 4F-PCC, respectively. For the overall population, the reported hemostatic efficacy was 65.4% (95% CI 55.4, 74.4) and 72.4% (95% CI 62.5, 81.0) for patients receiving FFP and 4F-PCC, respectively.

Also, in a study evaluating the efficacy of idarucizumab to reverse the effect of dabigatran [11, 26], the proportion of the overall patient population with an Investigator-assessed time to hemostasis less than 24 hours can be estimated to be approximately 66% (95% CI 59, 73). In addition, in 2 studies evaluating the efficacy of 4F-PCC in patients with FXa inhibitor-related major bleeding, hemostatic efficacy was reported as 69.1% (95% CI 58, 79) [27] and 84.8% (95% CI 74, 93) [28]. Gerner et al [8] investigated a total of 190 patients with intracerebral bleeding over a 5-year period treated with dabigatran (n=22), rivaroxaban (n=142), and apixaban (n=26). For these patients, the rate of hematoma expansion (defined as an increase from baseline of 33% or greater on follow up imaging) was observed to be 35% (therefore, 65% of patients did not have hematoma expansion). Finally, in a retrospective observational cohort of ICrH patients receiving PCCs, hemostatic efficacy was noted to be 81.8% in 433 efficacy evaluable patients [29].

For bleeding patients treated with andexanet, the FXa inhibitor reversal agent being evaluated in the current study, results from 477 patients enrolled in a Phase 3b/4 single arm, open-label study (ANNEXA-4) as of 30 June 2020 showed an effective hemostasis rate of 79% (95% CI of 74, 84) for 244 efficacy-evaluable patients with ICrH. Overall, for a total of 340 efficacy evaluable patients with all types of bleeding, the rate of effective hemostasis was 80% (95% CI of 75, 84).

The primary objective of this study is to compare the rate of effective hemostasis between andexanet and usual care in intracerebral hemorrhage patients. The statistical significance of the comparison will be evaluated by a two-sided test with the null hypothesis of no difference. Based on the hemostatic efficacy results discussed above, it is assumed that the rate of effective hemostasis in this study will be approximately 70% and 80% for patients treated with usual care and andexanet, respectively. The 10% absolute difference also represents a 33% risk reduction of not achieving effective hemostasis by andexanet as compared to usual care, such a magnitude is considered clinically meaningful. After accounting for early discontinuation rate and one interim analysis, it is estimated that a total sample size of approximately 900 patients (i.e., 450 patients per group) will have approximately 90% power to detect a 10% absolute difference between andexanet and usual care in the rate of effective hemostasis at a 0.05 two-sided overall significance level.

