	 Proportion of patients receiving rescue therapy between 3 and 12 hours post-randomization. 		
	• Correlation analysis between anti-fXa activity and the achievement of hemostatic efficacy.		
	• Health-related quality of life as assessed by the EuroQol-5 Dimension (EQ-5D) questionnaire at 30 days post-randomization.		
	 Utility-weighted Modified Rankin Scale (uw-mRS) score at 30 days post-randomization. 		
	Safety Endpoints		
	• Occurrence of TEs, confirmed by adjudication, through 30 days post-randomization.		
	• In-hospital mortality (during index hospitalization; all-cause, CV, and bleeding).		
	• 30-day all-cause, CV, and bleeding related mortality (defined as any death within 72 hours from randomization and not associated to the occurrent of an identified TE event).		
	 Proportion of patients with invasive intracranial procedures performed post-randomization to manage the intracranial hematoma and/or its complications. 		
	• Length of initial hospitalization for primary bleeding event.		
	• Total time admitted to the intensive care unit during the initial hospitalization.		
	• Proportion of re-hospitalizations, including total number of re-hospitalizations and total days re-hospitalized, at 30 days post-randomization.		
	• AEs and vital signs.		
	• Antibodies to Factor X (FX), FXa, and and exanet.		
	• Neutralizing antibodies to FX, FXa, and and exanet.		

Sample Size and Statistical Power	Approximately 900 patients (i.e., 450 patients per group) will be randomized 1:1 to receive either andexanet or usual care. After accounting for early discontinuation rate and the type I error associated with the interim analysis, this sample size should have approximately 90% power to detect a 10% absolute difference between andexanet and usual care_in the rate of effective hemostasis at an overall 0.05 two-sided overall significance level. The rate of effective hemostasis is estimated to be approximately 70% and 80% for usual care and andexanet, respectively. The expected rate of effective hemostasis in the andexanet population is based on efficacy results from ANNEXA-4. A 10% higher rate of effective hemostasis represents a 33% risk reduction of not achieving it from the usual care, which is considered clinically meaningful.			
Statistical Analysis	The primary objective of the study is to compare the proportion of patients with effective hemostasis (excellent or good as adjudicated by the blinded EAC) between and examet and usual care).			

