10.5.3.1. Primary Efficacy Endpoint

The primary efficacy endpoint is based on the achievement of effective hemostasis 12 hours post-randomization, as determined by the blinded EAC, based on pre-specified criteria documented in the Adjudication Charter (see Appendix B).

Effective hemostasis will be further defined as:

- 1 = for patients with hemostatic efficacy rated by the EAC as excellent or good, and
- 0 = for patients with hemostatic efficacy rated by the EAC as poor/none.

For a patient to have excellent or good hemostatic efficacy, he or she must meet all of the following criteria:

- NIHSS score of less than +7 point change from the baseline score at 12 hours post-randomization.
- No greater than 35% increase from baseline in hematoma volume within 12 hours post-randomization.
- Has not received rescue therapy (as defined in Section 7.2, Section 7.3, and Section 7.4) between 3 and 12 hours post-randomization

If data supporting either the imaging or clinical components of the adjudication of hemostatic efficacy are missing, out-of-window, uninterpretable or confounded (e.g., intubation or sedation), cases will be referred for external adjudication by EAC. Procoagulant blood products administered within 3 hours post-randomization to patients randomized to andexanet will be reviewed by EAC to determine if they were related to clinical or administrative reasons. Surgeries or procedures impacting hematoma volume within 3 hours post-randomization will also be reviewed by EAC to determine if related to clinical or administrative reasons (see Section 7.2, Section 7.3, and Section 7.4).

Cases where it is determined that there is insufficient information, or when it is not otherwise possible to properly assess the effect of treatment, will be further classified by the EAC as 'non-evaluable due to administrative reasons' (e.g., follow-up scan not available/ performed/ interpretable, patient transferred to another facility for administrative purposes) or 'non-evaluable due to clinical reasons' (e.g., patient died, patient had unplanned surgery draining hematoma).

All ITT patients will be included in the primary analysis. Patients with non-evaluable hemostatic efficacy due to clinical reasons will be treated as treatment failures (similar to patients with poor/none hemostatic efficacy). Both non-evaluable subjects due to administrative and clinical reasons will be included in the denominator for primary efficacy analysis.

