2. STATISTICAL HYPOTHESES

The primary objective of this study is to compare the rate of effective hemostasis between and exanet and UC group. The following hypothesis will be evaluated:

Ho:
$$\pi_{UC} - \pi_{andexanet} = 0$$

HA: $\pi_{UC} - \pi_{andexanet} \neq 0$

where π is the rate of effective hemostasis in each group.

Comparison will be performed using a Cochran-Mantel-Haenszel (CMH) test stratified by time from symptom onset to the baseline imaging scan (< 180 minutes versus \geq 180 minutes). The difference in the proportion of participants with effective hemostasis between andexanet and UC group, the corresponding 95% confidence intervals (CIs) for the difference, and the p-value for the comparison will be provided.

The analysis of efficacy will employ an alpha spending function by Lan and DeMets based on Pocock boundaries. The primary efficacy objective of the study will be considered met if the proportion of participants with effective hemostasis in the andexanet group is statistically significantly higher than that in the UC group at interim (p < 0.0310) or in the final (p < 0.0277) analysis.

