3. SAMPLE SIZE DETERMINATION

Results (as of 30 Jun 2020) from the Phase 3b/4, single-arm, open-label Study ANNEXA-4 have shown that the rate of effective hemostasis is 79% (95% CI: 74% to 84%) based on evaluable participants with ICrH; the rate of effective hemostasis is 80% (95% CI of 75% to 84%) based on 340 efficacy-evaluable participants with all types of bleeding.

Based on these results, it is assumed that the rate of effective hemostasis in this study is 70% and 80% for participants treated with UC and andexanet, respectively. The 10% absolute difference represents a 33% risk reduction of not achieving effective hemostasis by andexanet as compared to UC, which is considered clinically meaningful. After accounting for early discontinuation rate and one interim analysis, it is estimated that a total sample size of approximately 900 participants (ie, 450 participants per group) will have approximately 90% power to detect a 10% absolute difference between andexanet and usual care in the rate of effective hemostasis at a 0.05 two-sided overall significance level.

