5.3.1. Estimand

Table 3 below describes the attributes of the Primary (Composite) estimand.

Page 17 of 52 Alexion Confidential

Estimand	Attributes of Estimand				
	Treatment	Endpoint	Population	Intercurrent Events Handling	Statistical Summary
Primary (composite estimand)	Andexanet vs usual care	Proportion of participants with effective hemostasis	ITT Set	Rescue medications/procedures: All participants will be considered as poor/none (not effective) for effective hemostasis if meeting Criteria 1 and/or 2 below: 1. Initiation of rescue therapies (medication or procedures) starting ≥ 3 hours post- randomization and up to < 12 hours post-	Difference in the proportion of participants with effective hemostasis between the 2 treatment groups, and its 95% confidence interval as estimated by a CMH test stratified by the time from symptom onset to baseline imaging assessment (< 180 minutes vs ≥ 180 minutes)

Table 3:Attributes of Primary (Composite) Estimand

Estimand	Attributes o	of Estimand			
	Treatment	Endpoint	Population	Intercurrent Events Handling	Statistical Summary
				change from baseline to 12 hours in hematoma volume.	
				 Core imaging laboratory request for EAC review. 	
				4. Misadministration of procoagulant blood products contrary to treatment allocation within 3 hours pos-randomization (including andexanet in usual care arm)	
				5. Performance of a surgery or interventional procedure to treat the index hematoma or that could impact hematoma volume within 3 hours post- randomization	
				Nonevaluable events : There are 2 types of reasons for nonevaluable hemostatic status:	
				 Cases deemed nonevaluable due to administrative reasons (for example, but not limited to, follow-up scan not available, not performed not 	
				performed, not interpretable, or transfer of the participant to another facility for administrative purposes)	
				 Cases deemed nonevaluable due to clinical reasons (for example, but not 	

Table 3:Attributes of Primary (Composite) Estimand

Estimand	Attributes of Estimand					
	Treatment	Endpoint	Population	Intercurrent Events Handling	Statistical Summary	
				limited to, the participant died due to index bleed or the participant had unplanned surgery draining hematoma) The decision of the EAC is considered final. The nonevaluable status due to both reasons will be treated as poor/none in the primary analysis.		

 Table 3:
 Attributes of Primary (Composite) Estimand

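### The stated 90% power at 900 patients allows for discontinuation without saying how, while the primary analysis scores non-evaluable patients as failures; if 70% and 80% are evaluable-patient rates, 5% non-evaluable would give about 85%

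*Protocol*

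**What the plan says.** The power statement appears three times. Protocol 10.3: "a total sample size of approximately 900 patients (i.e., 450 patients per group) will have approximately 90% power", "at a 0.05 two-sided overall significance level". SAP 3 repeats that 900 "will have approximately 90% power to detect a 10% absolute difference", and the Synopsis says "this sample size should have approximately 90% power to detect a 10% absolute difference". All three say that early discontinuation and the interim analysis have been allowed for. None gives a discontinuation rate or the method of adjustment.

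The andexanet rate comes from a single-arm study: Protocol 10.3 reports 79% "for 244 efficacy-evaluable patients with ICrH" and 80% of 340 efficacy-evaluable patients with any type of bleeding. SAP 3 cites only these results before assuming 70% and 80%.

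The primary analysis uses the ITT set. Protocol 10.5.3.1 counts clinically non-evaluable patients as failures and adds: "Both non-evaluable subjects due to administrative and clinical reasons will be included in the denominator for primary efficacy analysis". SAP Table 3 is explicit for both kinds: "The nonevaluable status due to both reasons will be treated as poor/none in the primary analysis". SAP 6.1 repeats this. Success is declared "at interim (p < 0.0310) or in the final (p < 0.0277) analysis".

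**The concern.** A discontinuation allowance usually means dividing by the expected fraction retained: some patients are lost, n shrinks, and the assumed rates hold among those who remain. That does not fit this endpoint. A patient without an interpretable 12-hour scan or NIHSS score stays in the denominator and becomes a failure.

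If the planning rates describe evaluable patients, a non-evaluable fraction q multiplies both rates by (1 − q). The 10-point difference falls to 10 × (1 − q) points, and the variance rises as the rates move toward 50%. Each lost patient then costs more power than a dropped one. The 80% assumption is no lower than the 79% and 80% seen in evaluable patients, so it shows no sign of conversion to the ITT scale.

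At stake is how the 90% is read. The assumed rates, the 900 and the stated power should describe the analysis that will be run. If they do not, a non-significant result may be judged against a power that is too high. Type I error and the test itself are unaffected.

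**Working it through.** **Inputs.** Rates 70% and 80%, 450 per group, 1:1 allocation, two-sided overall alpha 0.05 (Protocol 10.2 and 10.3); nominal levels 0.0310 and 0.0277 (SAP 2); one interim look at half the patients (Protocol 10.7). The non-evaluable fraction q is not in the documents, so a range is shown.

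**Method.** For rates u (usual care) and a (andexanet), d = a − u and p̄ = (a + u)/2. Then s0 = √[2p̄(1 − p̄)] and s1 = √[a(1 − a) + u(1 − u)]. The critical values are c1 = 2.157 and c2 = 2.202. With n per arm:

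- b1 = (c1·s0 − d√(n/2))/s1 at the interim
- b2 = (c2·s0 − d√n)/s1 at the final
- power = 1 − P(X1 < b1 and X2 < b2), with X1 and X2 standard normal and correlation √0.5

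The two boundaries give an overall alpha of 0.04997, as intended.

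**Reproducing the plan's figure.** With u = 0.70, a = 0.80 and n = 450: s0 = 0.6124, s1 = 0.6083, b1 = −0.294, b2 = −1.271. Power is **90.9%** (91.1% by simulation). The stated figure therefore reproduces with no losses. The same calculation needs 872 patients for 90%, so the reserve in 900 is 900 − 872 = 28 patients.

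**Losses scored as failures.** At q = 5%, u = 0.70 × 0.95 = 0.665, a = 0.80 × 0.95 = 0.760 and d = 0.095. Then s0 = 0.6401, s1 = 0.6365, b1 = −0.070, b2 = −0.952, and power is **84.7%** (84.7% by simulation).

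**Losses dropped.** Rates stay at 70% and 80%, and n becomes 450 × (1 − q).

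| q (assumed) | Rates if scored as failures | Difference (points) | Power at 900, scored as failures | Power, same patients dropped |
|---|---|---|---|---|
| 0% | 70.0 / 80.0 | 10.0 | 90.9% | 90.9% |
| 1% | 69.3 / 79.2 | 9.9 | 89.8% | 90.6% |
| 2% | 68.6 / 78.4 | 9.8 | 88.6% | 90.3% |
| 3% | 67.9 / 77.6 | 9.7 | 87.3% | 90.0% |
| 5% | 66.5 / 76.0 | 9.5 | 84.7% | 89.4% |
| 10% | 63.0 / 72.0 | 9.0 | 77.6% | 87.7% |

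At 5%, dropping costs 90.9 − 89.4 = 1.5 points and scoring as failure costs 90.9 − 84.7 = 6.2 points. Most of the fall comes from the failure rule.

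**Some would have failed anyway.** If half of a 5% loss consists of patients already counted as failures in the planning rates, the diluting fraction is 2.5% and power is about 88%.

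**With re-estimation.** A simulation took the total to 1200 whenever conditional power under 80%/70% lay between 30% and 90%, and used the weighted statistic of Protocol 10.7.3. Power was about 91% at q = 5% and about 86% at q = 10%.

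**The case against.** The strongest reply is that nothing in the plan's arithmetic fails. The 90% reproduces, no non-evaluable fraction is stated, and at 1% to 2% the result still rounds to about 90%. Protocol 10.3 also presents 70% and 80% as the rates expected in this study. If they already count non-evaluable patients as failures, power is about 91%. This stands, and it is why the point is conditional. It does leave open what the separate discontinuation allowance is for.

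The 70% is less clearly an evaluable-patient rate than the 80%. Among the comparator sources in Protocol 10.3, only the retrospective PCC cohort is labelled efficacy-evaluable. This stands: the discount is well supported for andexanet and is an assumption for usual care.

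Some losses do shrink n. Patients randomized without ever signing consent are left out of the ITT set (Protocol 10.4.2, SAP 4), and deferred consent is allowed. This stands too, but such patients are not early discontinuations in the usual sense.

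Clinically non-evaluable patients, such as those who died or had the hematoma drained, would often have failed anyway. Administrative loss may be small for a 12-hour inpatient endpoint, because the EAC can accept out-of-window assessments. Both arguments reduce the size of the effect. Neither brings it to zero, and the SAP devotes sensitivity analyses 3 and 4 to administrative non-evaluability.

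Re-estimation can recover the loss at 5%. It can, but the stated power is for 900, and the increase happens only in the promising zone.

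**Conclusion.** The power statement does not match the primary analysis it describes. Its allowance for discontinuation is unexplained, and a dropping allowance is not what the ITT failure rule does. Nine hundred patients give 90.9% with no loss. If 70% and 80% are evaluable-patient rates and non-evaluability is equal across arms and unrelated to outcome, power at a fixed 900 is about 89%, 87%, 85% and 78% at 2%, 3%, 5% and 10% non-evaluable. Those fractions are assumed.

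A reader might infer that the trial simply lacks its 90% power. The documents do not support that: they give no q, they do not say which scale the rates are on, and the re-estimation is left out of the 900-patient figure. Nor can q be read from the single-arm study's 340 evaluable patients among 477 enrolled. The documents do not say why the others were not evaluable, and that study had its own criteria.

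**What to change.** In Protocol 10.3, the Synopsis and SAP 3:

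- Give the assumed non-evaluable fraction.
- Put both rates on the ITT scale, with non-evaluable patients counted as failures.
- Restate the power at 900. For example: with 5% of each arm non-evaluable and scored as poor/none, the expected rates are 66.5% and 76.0%, a difference of 9.5 points, and power at 900 is about 85% before any sample size increase.
- If 70% and 80% were meant as ITT rates from the start, say so and explain what the discontinuation allowance covers.

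Leave the sample size alone. Leave the 80%/70% assumption in the conditional-power rule (Protocol 10.7.2, SAP 5.9.2) alone as well: changing it would move the boundaries of the promising zone and so alter a prespecified adaptive rule.

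The cost is a few sentences in each document and a stated power that is likely to look less favourable.
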